**f. SCHEDULE OF ACTIVITIES**

Study Interval	Preoperative	Peri-operative	Post-Operative
	Screening	Date of Surgery	Follow-up Visits up to 3 months (0-90 days)
Review of demographics and preoperative variables (Table 1)	X		
Measurement of height, weight and BMI	X		
Screening—using eligibility criteria	X		
Patient Consent	X		
Preoperative image of scar	X		
Perioperative Values (Table 2)		X	
Postoperative Variables (Table 2)		X	X

**Table 2.** Collected peri- and post-operative variables

**Perioperative Variables**

Closure Time Incision Length Number of sutures used will be counted and recorded Any needle sticks or glove perforations Dressing Type Preoperative Incision Clinical Image
Postoperative Variables
Superficial wound complications: Skin irritation, erythema, suture spitting, cellulitis, superficial wound dehiscence, seroma, hematoma, prolonged wound drainage Deep wound complications: periprosthetic infection, arthrotomy failure, extensor mechanism failure Other non-closure associated complications Revision procedures for infection Revision procedures for any reason Post-operative antibiotic therapy Use of chronic antibiotic suppression therapy Post-operative Clinical Image (research only) POSAS Wound Score (research only)

## 10. STUDY DURATION

This study is designed as a prospective longitudinal study with participants remaining in the study for 3 months following revision total joint arthroplasty. Data collection for each individual study participant will be concluded at the 90-day post-surgical follow-up visit. Duration of the trial is expected to be two years in order to enroll an adequate number of patients and follow outcomes for at least 3 months postoperatively. The entire study is expected to last approximately 24 months.

## 11. DATA MANAGEMENT

Data will be collected and managed using REDCap. REDCap (Research Electronic Data Capture) is a secure, web-based application designed to support data capture. Monthly performance reports will summarize: patients recruited, patients successfully randomized, and the extent of follow-up for the enrolled patients. The reports also will evaluate the completeness of collected study data.

### Data Collection

After the patient has enrolled in this study, data will be directly collected from the patient and supplemented with electronic medical record (EMR) chart review. Additional data may be extracted from clinical notes. All members of the team will be trained in the reproducibly collection of clinical data. All data will then be input into REDcap. A member of the research team will be present at each patient follow-up to ensure that all necessary data points are collected. In addition, the research team may assist the physician when measuring the patient's functional outcomes.

## Reporting Requirements

### REDCap Features

- HIPAA-compliant and secure. Data are stored on a NYU server behind firewall.
- Intuitive, web-based interface for database build, data entry, and reporting
- Data validation, audit trail, branching logic, and calculated fields

- Data dictionary for easy project edits and duplication
- Automated data export (.csv, SPSS, SAS, Stata, R)
- Data import from external sources

## 12. STATISTICAL ANALYSIS

### Power Analysis

In our analysis if we assume an average length of closure of 30 minutes for revision with standard deviation of 5 minutes in closure time. The study is powered to compare hip and knee revisions separately. With an anticipated average decrease in closure time by five minutes, a minimum of 17 patients need to be included in each group (34 revision hips and 34 revision knees) will need be enrolled (power of 80% [alpha=0.025], one-sided). If we estimate a lost to follow up rate of 15% our recruitment goal will be set at 40 revision knees and 40 revision hips for a total of 80 revision total joints.

To perform our cost analysis, we assume a mean savings of \$200 with a standard deviation of \$50 (14). A minimum of 3 subjects per treatment group will need to be enrolled (power of 80% [one-sided alpha=0.025]). If we estimate a lost to follow up rate of 15%, we will have more than sufficient power with our recruitment goal at 80 enrolled patients, 40 revision TKA and 40 revision THA.

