### Statistical Analysis

Descriptive statistics will be used to report baseline characteristics as well as primary and secondary outcomes for the barbed suture and conventional cohorts. Outcomes will be compared between barbed suture and conventional closure (control) for the aforementioned baseline, perioperative and postoperative variables. Continuous or ordinal variables will be reported using unpaired t-tests, and all other categorical variables will be analyzed using Fisher's Exact Test. The test for primary endpoint will be one-sided (with the alternative hypothesis "mean closure time for barbed suture minus mean closure time for traditional suture <0") with a significance level of 0.025. Two-sided tests will be performed for baseline characteristics of patients and secondary endpoints with a significance level of 0.05. To further control for surgeon and evaluator variability we will also perform multivariable linear regression for continuous outcomes of interest and logistic regression for the dichotomous outcomes. Pooled and subgroup analysis for hip and knee revisions will be performed

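### Hip and knee closure times are sized as two separate comparisons, but the analysis states one primary test with no joint named and does not rank the pooled, hip and knee results

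*Combined protocol and SAP*

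**What the plan says.** All the relevant text is in Section 12 of the combined protocol and SAP.

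- **Power Analysis.** The sizing is by joint: "The study is powered to compare hip and knee revisions separately". It yields "a minimum of 17 patients need to be included in each group (34 revision hips and 34 revision knees", at 80% power and one-sided 0.025 for each joint, with no sharing of alpha between the two.
- **Statistical Analysis, primary test.** This is written in the singular: "The test for primary endpoint will be one-sided", at 0.025. The alternative hypothesis compares mean closure time for barbed and traditional suture and names no joint.
- **Statistical Analysis, by-joint work.** The only statement is "Pooled and subgroup analysis for hip and knee revisions will be performed". It gives no order, alpha split or success rule.
- **Statistical Analysis, method.** The default is "Continuous or ordinal variables will be reported using unpaired t-tests". The planned adjustment is "To further control for surgeon and evaluator variability we will also perform multivariable linear regression for continuous outcomes of interest", which names surgeon and evaluator but not joint.

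Other sections do not settle the matter. The primary objective (Section 2.2) and primary endpoint (Section 2.3) name no joint. Section 3.1 describes four arms, while Section 3.2.2 randomizes to two treatment groups and mentions no stratification by joint.

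**The concern.** The two halves of Section 12 describe different trials. The sizing implies two primary comparisons, one per joint. The analysis implies one primary comparison in an unnamed population, with hip and knee as subgroups. Three readings stay open: pooled primary, either joint suffices, or both joints must succeed. They differ in power and in error rate, and nothing written down would stop the choice from being made after the results are seen. The 80% in the Power Analysis belongs to none of the three as an overall success rate, so the plan states no power for the single primary test it describes.

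There is a smaller, related gap. If the pooled test is run as an unpaired t-test, any difference in mean closure time between hips and knees is left in the error term.

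**Working it through.** **Inputs from the Power Analysis.** "we assume an average length of closure of 30 minutes for revision with standard deviation of 5 minutes in closure time"; a 5-minute reduction; one-sided alpha 0.025; 17 per arm within each joint; 15% loss; 40 recruited per joint. The 20-per-arm figures below apply if all 40 patients per joint contribute a closure time.

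**1. Reproduce the plan's figure.** For a two-sample t-test, the noncentrality is δ / (σ√(2/n)).
- n = 17: 5 / (5 × √(2/17)) = 2.92, critical value 2.037 on 32 df, power 80.7%.
- n = 16: power 78.1%, so 17 is the minimum.
- Recruitment: 34 / 0.85 = 40 per joint, 80 in total.
- With 20 per arm, power is 86.9% per joint.

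**2. Power under each reading** (17 per arm per joint, 5 minutes in both joints, common SD, independent joints).

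| Reading | Calculation | Power |
|---|---|---|
| Pooled, 34 per arm | noncentrality 5 / (5 × √(2/34)) = 4.12 | 98.2% |
| Either joint suffices | 1 − (1 − 0.807)² | 96.3% |
| Both joints required | 0.807² | 65.1% |

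**3. One-sided error under each reading.**
- Pooled alone: 2.5%.
- Hip or knee, each at 0.025: 1 − 0.975² = 4.9%.
- Hip, knee or pooled, each at 0.025: about 5.8% to 6% by simulation.
- Both joints required: no inflation.

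**4. Two primaries under Holm at overall one-sided 0.025.** Power per joint at 0.0125 is 71.2% with 17 per arm and 79.3% with 20. Holm rejects for a joint if its p-value is at most 0.0125, or if it is at most 0.025 and the other joint's is at most 0.0125.
- Both joints benefit, 17 per arm: 0.712 + (0.807 − 0.712) × 0.712 = 78%.
- Both joints benefit, 20 per arm: 0.793 + (0.869 − 0.793) × 0.793 = 85%.
- Only one joint benefits: 0.712 + (0.807 − 0.712) × 0.0125 = 71% with 17 per arm, and by the same formula 79% with 20.

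**5. Plain t-test against joint in the model, for the pooled analysis at 17 per arm per joint.** The documents give one mean for both joints, so a hip-knee gap of 5 or 10 minutes is an assumption. With joint left out, the working SD is √(5² + (gap/2)²), which is 5.59 or 7.07.
- *Arms not balanced within joint (balanced overall):* noncentrality 5 / (5.59 × √(2/34)) = 3.69 or 5 / (7.07 × √(2/34)) = 2.92. Power is about 95% or 82%, and error stays at 2.5%.
- *Arms exactly balanced within joint:* the true standard error is 5 × √(2/34) = 1.213, but the test uses the inflated SD, so it rejects beyond about 2.71 or 3.42 minutes. Power is Φ((5 − 2.71)/1.213) = 97% or Φ((5 − 3.42)/1.213) = 90%. Simulated error is 1.4% or 0.3%.
- *Joint as a factor:* 98% power whatever the gap.

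**The case against.** The strongest reply is that the plan already implies a pooled primary. There is one objective, one endpoint and one hypothesis, and the hip and knee analyses are called subgroup analyses; the separate sizing then only ensures that each joint is informative. This is a fair reading, and it is why a pooled primary is offered below as a full alternative. It remains an inference, though. It would leave the sizing describing subgroup tests, with no power stated for the primary.

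A second reply is that hip and knee are separate questions with different closure techniques, as the four-arm description suggests, so no adjustment is needed. That is arguable, but the plan does not say it, and it sits badly with one primary test plus a pooled analysis.

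A third reply is that the practical effect is small under the planned assumptions. With a 5-minute effect in both joints, the pooled result (joint in the model) and an either-joint result disagree in only 3% of trials at 17 per arm and 1% at 20. This stands. Disagreement rises to 34% or 32% if only one joint benefits, but no section anticipates that.

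Three stronger inferences should not be drawn:

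- *That the trial runs at 5% to 6% one-sided error.* This needs a rule that any win counts, and the plan states none.
- *That the plain t-test is simply conservative.* This holds only with arms balanced within joint, and Section 3.2.2 describes no mechanism to secure that.
- *That frequent split hip/knee results prove the defect.* With both joints benefiting, exactly one is significant in 31% of trials (17 per arm) or 23% (20 per arm) unadjusted. Holm still leaves about 27% or 21%. The frequency mainly reflects roughly 80% power per joint.

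**Conclusion.** The concern holds as a mismatch within Section 12: the sizing and the stated primary test do not refer to the same comparison, and the pooled, hip and knee analyses are unranked. The sample size itself is correctly calculated for each joint alone. Depending on the rule adopted, power at 17 per arm runs from about 65% (both required) to 98% (pooled), and one-sided error from 2.5% or less to about 6% (any win). These figures assume the plan's SD of 5 minutes and its 5-minute effect in both joints, with hip and knee results independent. The plain t-test comparison also rests on an assumed hip-knee gap. The plan should be corrected before analysis; the mismatch does not invalidate the design.

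**What to change.** Make the two parts of Section 12 agree before analysis, by one of two routes. Both are defensible, and the choice is the sponsor's.

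**(a) Pooled closure time as the single primary at one-sided 0.025.** Hip and knee become secondary, or are tested in fixed sequence after it. Restate power as about 98% pooled (17 per arm per joint, common effect and SD) and 81% for each joint's test taken alone. In a fixed sequence, the joint placed last can be claimed only if the other also succeeds, so its power is at most about 0.807² = 65%. If only one joint benefits, pooled power with joint in the model falls to 50% (57% at 20 per arm).

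**(b) Hip and knee as the two primaries, with overall one-sided 0.025 controlled, for example by Holm.** The pooled result becomes supportive. Restate power as about 78% per joint at 17 per arm (85% at 20) if both benefit, and 71% (79%) if only one does. At 17 per arm this is below the plan's 80% target. Guaranteeing 80% at 0.0125 per joint would take 21 per arm: 42 per joint, 42 / 0.85 = 49.4, so 50 recruited per joint and 100 in total.

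**Under either route,** fit the pooled analysis as a linear model with joint as a factor, and add joint to the planned regression if it uses both joints. Joint is already known for every patient, and the term costs one degree of freedom.

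The change is a few sentences in Section 12. Route (a) needs no extra patients. Route (b) needs none only if the lower power is accepted.

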### Statistical Analysis

Descriptive statistics will be used to report baseline characteristics as well as primary and secondary outcomes for the barbed suture and conventional cohorts. Outcomes will be compared between barbed suture and conventional closure (control) for the aforementioned baseline, perioperative and postoperative variables. Continuous or ordinal variables will be reported using unpaired t-tests, and all other categorical variables will be analyzed using Fisher's Exact Test. The test for primary endpoint will be one-sided (with the alternative hypothesis "mean closure time for barbed suture minus mean closure time for traditional suture <0") with a significance level of 0.025. Two-sided tests will be performed for baseline characteristics of patients and secondary endpoints with a significance level of 0.05. To further control for surgeon and evaluator variability we will also perform multivariable linear regression for continuous outcomes of interest and logistic regression for the dichotomous outcomes. Pooled and subgroup analysis for hip and knee revisions will be performed

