### **2.3 ENDPOINTS**

#### *Primary Endpoint*

1. Measure the time needed to properly close the wound with each technique

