### 4.1. INCLUSION CRITERIA

1. Patients  $\geq$  18 years of age

2. Surgical candidates undergoing revision total knee or total hip arthroplasty for one of the following indications second stage of two stage reimplantation for infection, mechanical loosening, instability, polyethylene wear, stiffness, or periprosthetic fracture

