**c. PRE-OPERATIVE**

Once revision candidates have been identified and consented, patients will be randomized to traditional vs. barbed suture closure via RedCap. Medical records will be reviewed for baseline patient characteristics, preoperative patient data and laboratory values (Table 1). Prior to operation, a clinical image of the patients existing scar will be obtained for research purposes.

**Table 1.** Collected Baseline Patient Characteristics

Baseline Patient Characteristics
Age
Gender
Body mass index (BMI)
Zip code
American Society of Anesthesiologist (ASA) Score
Insurance type
Preoperative complete blood count (CBC), basic metabolic panel (BMP), and hemoglobin A1c (HbA1c)
Presence of diabetes mellitus
Cigarette smoking status
E-Cigarette smoking status
Immunocompromised status
Charlson Comorbidity Index (CCI)
Indication for Revision Arthroplasty

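### The primary closure-time test is unadjusted although BMI, indication and surgeon are known before closure; a short prespecified regression would be a cheap gain in precision

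*Combined protocol and SAP*

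**What the plan says.** The primary endpoint (section 2.3) is closure time: "Measure the time needed to properly close the wound with each technique". Section 12, Statistical Analysis, assigns continuous variables to unpaired t-tests and adds "The test for primary endpoint will be one-sided", at a significance level of 0.025. It then adds a regression: "To further control for surgeon and evaluator variability we will also perform multivariable linear regression for continuous outcomes of interest". That model has no covariate list, and surgeon and evaluator are the only factors mentioned.

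Section 4.1 admits six indications: "second stage of two stage reimplantation for infection, mechanical loosening, instability, polyethylene wear, stiffness, or periprosthetic fracture". Section 4.2 allows obesity. Section 3.2.1.1 leaves the intermediate layer in knees to the surgeon's discretion in both arms, with reference to thin patients. Table 1 in section 9.c lists BMI and "Indication for Revision Arthroplasty" among the baseline data. Section 3.2.2 describes no stratification factors.

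The Power Analysis treats hips and knees separately: "we assume an average length of closure of 30 minutes for revision", with a "standard deviation of 5 minutes in closure time", an expected reduction of five minutes and "power of 80% [alpha=0.025], one-sided". This gives 17 per group, raised to 40 knees and 40 hips for 15% loss.

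**The concern.** With 17 to 20 patients per arm in each joint, any spread in closure time that comes from known patient or surgeon characteristics stays in the error term of a t-test. A regression fixed in advance can remove part of that spread and correct for chance imbalance between arms, using data that the trial already collects.

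The documents give some reason to expect such spread. In knees, body habitus can change the number of layers closed, and so the endpoint itself. The background (section 1.1) says that closure is determined by surgeon preference and varies among surgeons. The plan acknowledges surgeon variability but deals with it only in an additional analysis. Because that analysis has no covariate list, its covariates could also be chosen after the data are seen.

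At stake is the precision of the primary comparison. Its validity is not in question.

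**Working it through.** **Inputs.** From the Power Analysis: difference 5 minutes, SD 5 minutes, one-sided alpha 0.025, 17 per arm per joint (minimum), 20 per arm (recruited). R-squared, the share of closure-time variance that the covariates explain within arm, is not in the documents. It is assumed from 0 to 0.4.

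**Step 1: the plan's own figure.** Power of the two-sample t-test comes from the noncentral t distribution with 2n − 2 degrees of freedom and noncentrality 5 / (5 × √(2/n)).
- n = 16: noncentrality 2.828, power 0.781.
- n = 17: noncentrality 2.915, critical value 2.037, power 0.807. So 17 is the smallest n that reaches 80%.
- n = 20: noncentrality 3.162, power 0.869.
- Recruitment: 34 / 0.85 = 40 per joint, 80 in total.

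The stated sample size is reproduced.

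**Step 2: adjusted power.** With k covariate degrees of freedom and N = 2n:
- residual SD = 5 × √(1 − R²)
- average variance inflation from chance covariate imbalance, V = 1 + k / (N − k − 3)
- noncentrality = 5 / (residual SD × √(2V/n)), on N − 2 − k degrees of freedom

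For k = 3, V = 1 + 3/28 = 1.107 at 17 per arm (29 df) and 1 + 3/34 = 1.088 at 20 per arm (35 df).

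| R-squared (assumed) | Power, 17 per arm | Power, 20 per arm |
|---|---|---|
| unadjusted t-test | 0.81 | 0.87 |
| 0 | 0.76 | 0.84 |
| 0.1 | 0.81 | 0.87 |
| 0.2 | 0.85 | 0.91 |
| 0.3 | 0.89 | 0.94 |
| 0.4 | 0.93 | 0.97 |

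**Step 3: break-even.** Adjustment pays once (1 − R²) × V falls below 1, that is, once R² exceeds about k / (N − 3). For k = 3 at 17 per arm this is 3/31 = 0.097; allowing for the lost degrees of freedom it is 0.10. A longer list moves it up: for k = 6, 6/31 = 0.19. The covariate set should therefore be short.

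**Step 4: if 5 minutes were the SD within an indication.** Suppose indications differ with an SD of b minutes (assumed). The total SD is then √(25 + b²), and unadjusted power is:

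| b | Total SD | 17 per arm | 20 per arm |
|---|---|---|---|
| 2 | 5.39 | 0.75 | 0.82 |
| 3 | 5.83 | 0.68 | 0.75 |
| 4 | 6.40 | 0.60 | 0.67 |
| 5 | 7.07 | 0.52 | 0.59 |

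If grouping the indications captures half of that variance (assumed), the residual SD is √(25 + b²/2). Power at 17 per arm with three degrees of freedom deducted, and imbalance not charged, is then 0.77, 0.74, 0.69 and 0.63. The objection explains why this step is not the basis of the conclusion.

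**The case against.** The strongest reply is that nothing is wrong. An unadjusted t-test is valid in a randomised trial, and its standard error already allows for chance imbalance. The sample size is right. Regression is planned for continuous outcomes, which plausibly include closure time, and an open covariate list does not exclude BMI or indication. All of this stands. What remains is that the adjusted analysis is secondary and its covariates are not fixed.

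A reader might infer from step 4 that the trial is underpowered because it mixes six indications. The documents do not support that:
- The 5-minute SD is given for revisions generally. It reads more naturally as the total SD, case mix included, and power is then 0.81.
- The lowest figure needs indication to explain 25/50, or half, of all variance.
- No figure shows that indication predicts closure time. The endpoint is wound closure and not operative time, closure is specified by layer whatever the indication, and section 4.2 excludes plastic-surgeon and flap closures and stage 1 revisions.

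Closure time is also recorded in surgery, so loss to follow-up should hardly affect it. The evaluable number may be near 20 per arm, although section 5.1 withdraws patients for deviation from the closure protocol.

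A model with BMI and indication alone would leave out surgeon, which is the source of variation that the documents themselves name. That criticism is right, and the fix includes surgeon.

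**Conclusion.** The point holds as a precision gain. The primary test leaves out covariates that are known before closure, and the additional regression does not fix them in advance. With three covariate degrees of freedom at 17 per arm, adjustment moves power from 0.81 to between 0.76 and 0.93 as R-squared goes from 0 to 0.4. At 20 per arm it moves from 0.87 to between 0.84 and 0.97. The gain starts at an R-squared of about 0.10.

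This rests on the plan's SD of 5 minutes, on the assumed R-squared range, and on three covariate degrees of freedom. Support for BMI comes from the discretionary layer in knees only. Support for surgeon comes from the plan's own text. For indication it is only an inference from the eligibility list.

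Two further inferences should be resisted. Adjustment is not free, since it loses power when the covariates explain little. Nor does it make good the missing source for the 5-minute SD: if the true SD were 7, R-squared would have to be 1 − 25/49 = 0.49 to bring the residual SD back to 5.

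**What to change.** Amend section 12, Statistical Analysis. Within each joint, make the primary analysis a linear regression of closure time on arm with a short covariate set fixed before any outcome data are examined:
- BMI, continuous;
- surgeon, in the form already intended for the planned regression, with low-volume surgeons grouped by a stated rule;
- if wanted, indication in two or three classes defined in advance.

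Test the arm coefficient one-sided at 0.025, and keep the unpaired t-test as a supportive analysis. Incision length is recorded perioperatively, after allocation, so it belongs only in a prespecified sensitivity analysis.

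The cost is SAP wording and a few degrees of freedom per joint, with no new data, patients or procedures. The downside is the small power loss below an R-squared of about 0.10 (at worst 0.81 to 0.76 at 17 per arm with three degrees of freedom). The documents do not give the number of surgeons, so the grouping rule should keep the total near three degrees of freedom. This is a cheap improvement.

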#### *Secondary Endpoints*

1. Record all complications (including needle sticks and glove perforations) and infections related to the wound closure
2. Calculate the cost difference based on supplies, personnel, and OR time between each technique
3. Gather pictures of wound following closure to evaluate the cosmetic result of barbed versus traditional suture in revision total joint arthroplasty using the Patient and Observer Scar Assessment Scale (POSAS)
4. Calculate the number of suture used and length of incision for each technique

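### Ordinary logistic regression with surgeon adjustment is planned for every dichotomous outcome, with no sparse-data method for outcomes that turn out to be uncommon

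*Combined protocol and SAP*

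**What the plan says.** The whole treatment of dichotomous outcomes is in Section 12, Statistical Analysis. The unadjusted comparison is that "all other categorical variables will be analyzed using Fisher's Exact Test", two-sided at 0.05 for secondary endpoints. A regression layer is then added: "To further control for surgeon and evaluator variability we will also perform multivariable linear regression" for continuous outcomes, and "logistic regression for the dichotomous outcomes". The section closes with "Pooled and subgroup analysis for hip and knee revisions will be performed". That sentence is not limited to any one method, so I read it as covering the regressions too.

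The outcomes come from Section 2.3, Secondary Endpoints ("Record all complications (including needle sticks and glove perforations) and infections related to the wound closure"), and from the follow-up list in Section 9. That list runs from extensor mechanism failure and deep infection to erythema, skin irritation and wound drainage. The recruitment goal in Section 12, Power Analysis, is "40 revision knees and 40 revision hips for a total of 80 revision total joints".

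The plan does not state an expected rate for any dichotomous outcome, how many surgeons or evaluators take part, whether surgeon is a fixed or random term, a minimum number of events for fitting a model, or what replaces the model if it cannot be fitted.

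**The concern.** Maximum-likelihood logistic regression has no finite solution when some combination of covariates predicts the outcome perfectly (separation). With fixed surgeon terms, one surgeon with no events is enough to send that surgeon's coefficient to minus infinity. One closure arm with no events does the same to the treatment coefficient, and then there is no usable adjusted odds ratio or Wald interval for barbed against conventional closure.

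The sample size was set for closure time and cost, so nothing in the design secures enough events for these models. The outcomes most likely to be sparse are the serious ones. Section 2.1 frames the aim as a faster closure that does not worsen wound complications, Section 1.1 acknowledges that closure practice varies between surgeons, and Section 3.2.2 describes no stratification by surgeon. An adjusted complication result would therefore attract interest. With no fallback written down, a model that fails would have to be abandoned or changed once the data are in hand.

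**Working it through.** **The plan's own figure.** Section 12, Power Analysis, assumes a 5-minute difference, SD 5 minutes, one-sided alpha 0.025 and 80% power. The exact t-test calculation gives power 0.781 at 16 per group and 0.807 at 17, so the stated 17 reproduces. With 15% loss, 34/0.85 = 40 per joint and 68/0.85 = 80 in total. These figures say nothing about dichotomous outcomes.

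**Inputs for the check.** From the documents: 80 pooled, 40 per joint, and ordinary logistic regression. Assumed, because the documents give no figure: event rate 2% to 20%, 2 to 8 surgeons, fixed surgeon terms, patients spread at random over surgeons, equal allocation (40 per arm pooled, 20 per arm within a joint), and no true treatment or surgeon effect.

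**Step 1: an arm with no events.** With n patients per arm and event rate p, P(at least one arm has none) = 1 − [1 − (1 − p)^n]².

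- Pooled, n = 40, p = 5%: 0.95^40 = 0.129; 1 − 0.871² = 0.24.
- One joint, n = 20, p = 5%: 0.95^20 = 0.358; 1 − 0.642² = 0.59.
- Pooled, p = 10%: 0.9^40 = 0.015; 1 − 0.985² = 0.03.
- One joint, p = 10%: 0.9^20 = 0.122; 1 − 0.878² = 0.23.
- After the planned 15% loss, p = 5%: n = 34 gives 0.32 and n = 17 gives 0.66.

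**Step 2: a surgeon with no events.** At 5%, 80 patients yield about 4 events and 40 yield about 2. Four events cannot cover five surgeons, nor two events three surgeons. With five equal surgeons pooled (16 patients each), 0.95^16 = 0.440, and P(at least one surgeon has none) = 1 − (1 − 0.440)^5 = 0.945.

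**Step 3: simulation.** There were 300 trials per cell. The model had arm and surgeon indicators, plus a joint term when pooled. Linear programming detected separation anywhere in the model and, separately, a non-finite treatment coefficient. Cells show P(any separation) / P(treatment odds ratio non-finite).

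| Set | Surgeons | 2% | 5% | 10% | 20% |
|---|---|---|---|---|---|
| Pooled, 80 | 2 | 0.82 / 0.65 | 0.42 / 0.24 | 0.08 / 0.03 | 0.00 / 0.00 |
| Pooled, 80 | 3 | 0.96 / 0.71 | 0.67 / 0.20 | 0.23 / 0.02 | 0.01 / 0.00 |
| Pooled, 80 | 5 | 1.00 / 0.69 | 0.94 / 0.20 | 0.70 / 0.04 | 0.21 / 0.00 |
| Pooled, 80 | 8 | 1.00 / 0.71 | 1.00 / 0.26 | 0.99 / 0.03 | 0.63 / 0.00 |
| One joint, 40 | 2 | 0.95 / 0.90 | 0.69 / 0.55 | 0.31 / 0.24 | 0.03 / 0.02 |
| One joint, 40 | 3 | 0.99 / 0.88 | 0.91 / 0.57 | 0.62 / 0.21 | 0.20 / 0.02 |
| One joint, 40 | 5 | 1.00 / 0.92 | 1.00 / 0.60 | 0.95 / 0.23 | 0.67 / 0.03 |
| One joint, 40 | 8 | 1.00 / 0.88 | 1.00 / 0.60 | 1.00 / 0.31 | 0.99 / 0.03 |

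The Monte Carlo standard error is at most about 3 points (√(0.5 × 0.5/300) = 0.029). Repeat runs of the same set-up moved cells by a few points: with three surgeons pooled at 5%, any separation was 63%, 67% and 70%. The ranges quoted in the conclusion include those runs. The treatment column tracks the closed form in step 1, and the five-surgeon separation figure tracks step 2.

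**The case against.** A reader might infer that adjusted odds ratios for complications will usually be infinite or meaningless. The documents and the calculation do not support that. Separation somewhere in the model and failure of the treatment estimate are different events. A surgeon with no events drops out of the information on treatment, and the treatment odds ratio is normally estimated from the remaining surgeons. With five surgeons pooled, the two probabilities are 94% and 20% at a 5% rate, and 70% and 4% at 10%. A non-finite treatment odds ratio becomes the likelier result only at about 3% or less pooled (45-55% at 3%), or about 5% or less within one joint.

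Four further points stand:

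- Nothing in the documents calls these outcomes rare. Several listed ones, such as erythema or drainage, could be common. The suspension thresholds in Section 15 are not expected rates.
- Fixed surgeon terms are an inference from "To further control for surgeon and evaluator variability"; a random effect fits the wording and would behave differently. The only observer rating the documents name is the POSAS observer scale, which is not dichotomous, so an evaluator term for infection or needle sticks is also a reading.
- Fisher's exact test is the planned comparison and remains valid with an empty cell. The regression is additional, and the plan does not rest its complication conclusion on an adjusted odds ratio.
- The primary endpoint is continuous and untouched.

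These points limit the reach of the concern. They do not supply the missing method for the outcomes that do turn out sparse.

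**Conclusion.** The point holds for low-incidence dichotomous outcomes, as a gap in a supplementary secondary analysis. Assuming fixed surgeon terms and 3 to 8 surgeons, a 5% event rate gives separation somewhere in the model in about 63-100% of pooled trials and over 90% of single-joint trials. The treatment odds ratio is non-finite in about 20-26% of pooled and 55-63% of single-joint analyses at 5% (the 55% is the two-surgeon case), and in about 2-5% and 21-35% at 10%. At 20% or more it is finite in at least 97% of the simulated trials.

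Event rates, number of surgeons, coding of surgeon and equal allocation are all assumptions. The zero-event-arm part does not depend on the number of surgeons or on how surgeon is coded. The separation figures do.

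**What to change.** In Section 12, Statistical Analysis, for low-incidence dichotomous outcomes:

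1. Replace ordinary maximum-likelihood logistic regression with Firth penalised-likelihood logistic regression, with profile penalised-likelihood intervals. Surgeon may stay in the model, so the purpose of the adjustment is kept. The joint term belongs only in the pooled analysis.
2. Report the risk difference between arms with an exact or score 95% interval beside Fisher's p-value. This remains available when an arm has no events.
3. Define low incidence before the data are seen, by naming the outcomes or by a total event count over both arms, and state how surgeon is coded.

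Common outcomes need no change. The cost is a few lines of plan wording, standard software and slightly more analysis work. The downside is some shrinkage of the adjusted estimates. Firth's method keeps them finite but cannot add information, so intervals will still be wide where events are few. Sample size and trial procedures are unaffected. Label: cheap improvement.
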